# Oral Acetaminophen Risks

Acetaminophen is generally considered to be safe to use during pregnancy and has been categorized as Class B for all trimesters. Acetaminophen is known to cross the placenta during pregnancy, and acetaminophen administered during labor has been found in the umbilical cord blood at delivery (Levy 1975). There is no known association with teratogenicity, however few clinical studies have assessed safety (Collins 1981). More recent studies with poor power have suggested a link between prenatal acetaminophen use and asthma, lower intelligence quotient,

\*See Separate Section for management of adverse reactions

shorter male anogenital distance (predicting poor male reproductive potential), attention-deficit/hyperactivity disorder, poorer attention and executive function, and behavioral problems in childhood (Toda 2017). The Society of Maternal Fetal Medicine deems these studies as inconclusive as the methodologies were subject to recall bias and no data on dosing or frequency of use was incorporated into the analyses (Society of Maternal Fetal Medicine 2017). Thus, the current recommendation is to use acetaminophen for at the lowest dose for the minimal duration possible. We will be administering a single 650mg dose of acetaminophen in the course of this study, which is considered to be safe in pregnancy.

Adverse effects of oral acetaminophen include nausea, vomiting, abdominal pain, loss of appetite, itching, rash, headache, dark urine, clay-colored stools, or jaundice. Serious allergic reactions to acetaminophen can include rash, itching/swelling (including of the face/tongue/throat), severe dizziness, or difficulty breathing.

#### 2.3.3 Risk Benefit/Ratio

Iron deficiency anemia at admission for birth hospitalization has been associated with increased severe maternal morbidity, preterm birth, low birth weight, incidence of C-section and more. Assessment of outcomes in this study will determine how treatment can improve maternal and neonatal outcomes.

# 3. OBJECTIVES

# 3.1 Primary Outcome

**Perform a pilot randomized control trial of oral ferrous sulfate to IV ferumoxytol in women with IDA in the second and third trimester of pregnancy.** We will *test the hypotheses* that 1) intravenous (IV) iron therapy will increase hemoglobin more with IV iron than oral iron over a 4 week period, approximately 0.8 g/dL in the IV group and 0.5g/dL in the oral arm  and 2) IV iron will improve anemia at the time of birth admission, 1.5 g/dL for IV iron and 1 g/dL for oral iron supplementation, the standard of care

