# **Inclusion Criteria:**

- 1. Pregnant patients 18 years old and above receiving prenatal care at Stanford/LPCH OB clinic
  - a. Hemoglobin < 11 g/dL, serum ferritin < 30 ug/dL and or transferrin saturation (TSAT) < 20%
  - b. Between 24-34 weeks' pregnancy
  - c. (study will offer iron studies to determine eligibility for patients eligible by hemoglobin if labs not ordered by primary obstetrician/health care provider per standard of care)
- 2. Singleton pregnancy
- 3. Viable Pregnancy
- 4. Hemodynamically stable

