# 5.4 Screening/Re-screening

Patients may be included in the study up to 34 weeks 6/7 days. If the above inclusion criteria are met and exclusion criteria are absent, patients should be approached for study participation (if not already done) and randomization. All women who have a diagnosis of IDA should have the screening form initiated. The screening number will be generated electronically with REDCap is accessed and participant information is entered.

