# 5.9 Frequency of Labs

The timing of follow up labs is determined by the expected amount of time a participant should see an increase in hemoglobin. The hypothesis is that 1) intravenous (IV) iron therapy will increase hemoglobin more with IV iron than oral iron over a 4 week period, approximately 0.8 g/dL in the IV group and 0.5g/dL in the oral arm and 2) IV iron will improve anemia at the time of birth admission, 1.5 g/dL for IV iron and 1 g/dL for oral iron supplementation, the standard of careThe estimates are informed from a 2018 study which reflected a 1.5 g/dL increase in hemoglobin by time of delivery in the intravenous group.

The follow up and reassessment is further informed by Micheal Auerbach's et al approach to treatment of IDA in pregnancy.

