#### After randomization:

- Provide medication and instructions based on the treatment arm randomized to
- Provide the group algorithm to both patient and provider.

Once the participant is randomized, the treatment algorithms will be conspicuously placed in the patient's medical record (whether electronic or paper medical record is utilized) such that providers will be aware of treatment plan at all times.

In both groups, serial CBC follow up and survey for symptoms will be assessed. Baseline data consisting gestational age of pregnancy, body mass index, pre-pregnancy weight and other prenatal data including baseline BP at the randomization visit will be included. Patients will be assigned to treatment groups by a concealed randomization allocation sequence using REDCap.

The categories of patients randomized:

Patients consenting to the study will be randomized 1:1 to two treatment groups

Group 1: Patients randomized to the IV iron group will receive treatment as follows:

- Women with Hgb 9-10.9 g/dL will receive one dose of 510 mg IV ferumoxytol
- Women with Hg 7-8.9 d/dL will receive two doses of ferumoxytol 510 mg 3-8 days apart for a maximum of dose of 1020 mg (see **Figure 2**).
- Patients will receive 650mg of Tylenol prior to initiation of the infusion
- The ferumoxytol is administered as an infusion for approximately 15-30 minutes. Patients will receive the IV iron at Stanford's Clinical and Translational Research Unit (CTRU) outpatient clinics with vitals collected before infusion and monitoring for 30minutes after infusion. Alternatively, patients who are admitted to the antepartum unit may receive the infusion inpatient.

For the IV iron group, follow up labs will be performed at 4 and 8 weeks after completion of infusion/s;

Group 2: The standard of care oral iron group will be prescribed 1-2 ferrous sulfate 325 mg tablets to be taken by mouth **every other day** until delivery. Dosage will be as follows for standardization:

- one ferrous sulfate tablet every other day if Hg 9-10.9 g/dL, and
- two tablets once every other day if Hg 7-8.9 g/dL.
- Oral medications will be dispensed by the CTRU or by the Outpatient Investigational Pharmacy (final confirmation pending contracts)
- Follow up labs will be drawn for both groups. For the oral iron group, it will be drawn 4- and 8-weeks post initiation of treatment

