#### 12. STATISTICAL ANALYSIS

#### 12.1 Statistical Considerations

Efficacy Endpoint(s): The primary outcome for this study is to assess the delta in hemoglobin pre and post intervention in both treatment groups. Our hypothesis is that the rate of increase of intravenous iron will be approximately 1.5g/dL higher in the IV iron cohort versus the oral iron cohort

Secondary Efficacy Endpoint(s): The secondary outcomes for this study include the following:

- correction of anemia at the time of birth hospitalization,
- rates of blood transfusion,

- neonatal outcomes such as APGARs and NICU admissions
- maternal/neonatal infection
- mode of delivery (NTSV)
- infant birth weight

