# 12.3 Analyses

We will conduct an intent-to-treat analysis to compare the primary and secondary outcomes between the treatment arms. The primary outcome is the mean change in hemoglobin in oral vs IV iron over 4 weeks as well mean change in hemoglobin pre delivery. The primary outcome will be assessed using t-tests. Baseline characteristics between the groups will be compared using t-tests and chi-square tests. If there is an imbalance between the treatment arms, we will use multivariable regression modeling. Differences will be considered statistically significant at P<0.05.

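### The birth-admission comparison pools roughly 4 to 15 weeks of treatment, and 12.3 does not pre-specify adjustment for gestational age at entry

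*Combined protocol and SAP*

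**What the plan says.** Section 3.1 gives two hypotheses on mean hemoglobin change. Over 4 weeks it expects "approximately 0.8 g/dL in the IV group and 0.5g/dL in the oral arm". At birth it expects that "IV iron will improve anemia at the time of birth admission, 1.5 g/dL for IV iron and 1 g/dL for oral iron supplementation". Section 5.9 repeats both and gives a source for the intravenous figure: "The estimates are informed from a 2018 study which reflected a 1.5 g/dL increase in hemoglobin by time of delivery in the intravenous group". Neither section says how many weeks of treatment, or what gestational age at entry, the birth values refer to.

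The synopsis inclusion criteria set entry at "Between 24-34 weeks' pregnancy". Section 5.4 states: "Patients may be included in the study up to 34 weeks 6/7 days". Sections 5.1 and 5.6 say 34 weeks, section 7.9.1 allows the randomization sample up to 32 weeks, and section 7.7 says 30 completed weeks. Section 1.1.2 prefers 24-28 weeks for the baseline labs.

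Section 12.3 makes change over 4 weeks and change before delivery the primary outcome. On the method it says: "The primary outcome will be assessed using t-tests". Multivariable regression follows only when the arms turn out unbalanced, and no covariates are named. Section 6 already collects the relevant variable: "Baseline data consisting gestational age of pregnancy, body mass index, pre-pregnancy weight".

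**The concern.** For change to birth admission, the plan does not fix the time on treatment. Gestational age at entry largely sets it. A woman who enters in the last permitted week has her birth blood count at about the point where the plan itself expects a difference of 0.3 g/dL. A woman who enters at 24 weeks has nearly four times as long. One pair of expected gains is stated for both.

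Two things are at stake. The first is interpretation: a small pooled difference at birth could reflect late entry as well as a weak effect, and the plan gives no way to tell. The second is precision: a two-sample t-test on raw change treats the spread in gain that comes from entry time as unexplained noise, although a baseline variable that predicts it is on file. Leaving adjustment to depend on observed imbalance also makes the primary model a decision taken after the data are seen.

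**Working it through.** **Plan's own figures.** At 4 weeks: 0.8 − 0.5 = 0.3 g/dL. At birth: 1.5 − 1.0 = 0.5 g/dL. Section 12.1 instead expects an increase "approximately 1.5g/dL higher in the IV iron cohort versus the oral iron cohort", which conflicts with 0.5. I use the 3.1 and 5.9 values. The 32 per arm in 4.4 and 12.2 cannot be reproduced: it rests on the share of women below 11 g/dL at birth, the two proportions are not given, and no SD is stated anywhere.

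**Exposure.** Weeks to birth = gestational age at birth − gestational age at entry. With birth at 39 weeks (assumption):
- entry at 24 0/7: 39 − 24 = 15 weeks
- entry at 28 0/7: 39 − 28 = 11 weeks
- entry at 34 6/7: 39 − 34.86 = 4.1 weeks (2.1 if birth is at 37 weeks, 5.1 if at 40)

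**Expected difference if 1.5 and 1.0 describe early entrants.** Assume that the difference grows linearly from 0.3 at week 4 to 0.5 at week T and is flat afterwards: d(w) = 0.3 + 0.2 × (w − 4)/(T − 4) for 4 ≤ w ≤ T. T is not in the documents. I take 8 weeks (the last scheduled antenatal lab) to 15 weeks (the longest exposure).

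Uniform entry from 24 0/7 to 34 6/7, birth fixed at 39 weeks, so w is uniform on 4.14 to 15:
- T = 15: mean w = 9.57, so d = 0.3 + 0.2 × 5.57/11 = 0.401.
- T = 8: for w from 4.14 to 8 (3.86 weeks), mean d = 0.3 + 0.2 × 2.07/4 = 0.404. For the other 7 weeks d = 0.5. Average = (3.86 × 0.404 + 7 × 0.5)/10.86 = 0.466.

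Entry at 24-28 weeks, w uniform on 11 to 15:
- T = 15: 0.3 + 0.2 × 9/11 = 0.464.
- T = 8 or 11: 0.500.

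A simulation with birth at 39 weeks, SD 1.3 (assumed), gives 0.40-0.46 for uniform entry and 0.46-0.50 for entry at 24-28 weeks. Sensitivity with the birth date fixed and T = 8 to 15: if 70% enter at 24-28 weeks (assumed), 0.43-0.48; uniform entry with birth at 37 weeks, 0.36-0.42; with birth at 40 weeks, 0.42-0.48.

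**Power, with and without gestational age in the model.** Let σ be the residual SD (assumed 0.7 or 1.0) and v the within-arm variance in expected gain due to exposure, averaged over arms. SE = √(2(σ² + v)/n). Power comes from the non-central t at two-sided 0.05 with 2n − 2 df. With the covariate, v is replaced by what remains after a linear term in gestational age at entry, with 2n − 3 df.

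Example, uniform entry, T = 13, σ = 0.7, n = 40: the exposure SD is 0.244 (IV) and 0.173 (oral), so v = (0.0595 + 0.0299)/2 = 0.0447. SE = √(2 × 0.5347/40) = 0.1635, d/SE = 0.416/0.1635 = 2.54, and power is 71.0%. With the covariate it is 74.0%.

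Uniform entry, 40 per arm, birth SD 1.3 weeks:

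| T (weeks) | Difference | σ = 0.7: t-test → adjusted | σ = 1.0: t-test → adjusted |
|---|---|---|---|
| 8 | 0.461 | 79.7 → 81.2% | 51.4 → 52.2% |
| 11 | 0.434 | 74.4 → 77.2% | 46.6 → 47.8% |
| 13 | 0.416 | 71.0 → 74.0% | 43.6 → 44.8% |
| 15 | 0.399 | 67.9 → 70.5% | 40.9 → 41.9% |

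For comparison, a constant 0.5 g/dL with no exposure variance gives 88.4% (σ = 0.7) and 59.8% (σ = 1.0). With 32 evaluable per arm (40 less 20%), the adjustment gains 1.6-3.0 points at σ = 0.7 and 0.7-1.1 at σ = 1.0. For entry at 24-28 weeks the change is between −0.1 and +0.3 points.

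**The case against.** The strongest reply is that 1.5 and 1.0 are stated as averages at birth admission. If the earlier studies enrolled over a range of gestational ages, those averages already contain late entrants and nothing is diluted. The plan does not describe those studies' entry windows, so neither reading can be shown. This stands.

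The size is also conditional. Uniform entry to 34 6/7 is pessimistic: recruitment runs mainly off the routine 24-28 week blood count, although other blood counts and re-screening allow later entry. Under uniform entry with birth at 39 weeks, only 0.857/10.857 = 8% would have under 5 weeks. The choice of SD moves power by about 29 points (88.4% to 59.8%), more than any dilution here. This stands too, and it rules out a single corrected effect.

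A reader might infer that the t-test is biased. It is not. Randomization balances gestational age in expectation, so the test estimates the average effect in the women enrolled. A reader might also infer that the planned number is too small. The documents do not show that, because 32 per arm was derived from proportions, not from 1.5 versus 1.0.

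Finally, adjustment recovers little, because any loss comes mainly from a smaller mean difference, which no covariate restores. That is true. The case for adjustment is that it costs almost nothing and removes a data-dependent choice.

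**Conclusion.** The point holds in a limited form. The birth-admission contrast pools women with about 4 to 15 weeks from entry to birth (birth near 39 weeks assumed), and the plan's own figures imply a difference that grows with time, from 0.3 to 0.5 g/dL. If 1.5 and 1.0 refer to early entrants, the average difference at birth is about 0.40-0.50 g/dL, depending on how many enter late and how soon the full effect is reached. If they already average mixed entry, it stays at 0.5. The documents do not decide between these.

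It is tempting to conclude that the plan assumes an exposure late entrants cannot have, and that the true figure is 0.40-0.43. The documents do not support this: no section ties the birth values to a full exposure, and that range needs uniform entry, linear growth and a full effect only at 11-15 weeks or later.

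What remains is a missed improvement: a prognostic baseline variable, already collected, is left out of the primary model unless imbalance is seen. Its value is about 0-3 points of power at assumed SDs of 0.7-1.0, plus a model fixed in advance.

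**What to change.** In 12.3, analyse change to birth admission with a pre-specified linear model containing treatment and gestational age at randomization as a continuous covariate, always included, together with any other baseline terms planned. This replaces the imbalance-triggered regression for this contrast. Do not adjust for observed weeks to birth, which arises after randomization and could be affected by treatment.

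Optionally, report the treatment difference by gestational age at entry, labelled descriptive, because 80 women will estimate it imprecisely.

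Reconcile the upper entry limits in 5.4 (34 6/7 weeks), the synopsis, 5.1 and 5.6 (34 weeks), 7.9.1 (32 weeks) and 7.7 (30 weeks). Do not write 0.40-0.43 g/dL into 3.1 or 5.9 as the expected difference, because it depends on assumptions outside the documents.

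Cost: a wording change and one degree of freedom (78 to 77 with 40 per arm). No new data are needed. If nearly all women enter at 24-28 weeks, the gain in power is essentially nil, and the benefit is only that the model is fixed in advance.

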#### 3.2 Secondary Outcome

Evaluate the

- rate of patients who discontinued treatment,
- the rate of adverse events associated with treatment,
- the need for blood transfusion postpartum
- symptoms of patients before, during, and at the completion of therapy

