# Primary safety outcome:

- O Rates of adverse events
- o Compliance with medication
- o Severe neonatal composite morbidity
- o Severe maternal morbidity

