#### 4. STUDY DESIGN

#### 4.1 Overall Design

This will be an open-label randomized clinical trial at an academic tertiary care center comparing oral ferrous sulfate to intravenous (IV) ferumoxytol in pregnant women with IDA in the second or third trimester.

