# **6. RANDOMIZATION AND BASELINE VISIT PROCEDURES**

In participants with IDA prior to 24 weeks' gestation, they can still be included in the study if they meet the inclusion criteria at 24 weeks gestation/ enrollment time frame. If IDA is a new diagnosis at the time of 24-28 weeks gestation, patients meeting the inclusion criteria be included.

In both groups, prenatal data will be obtained at the randomization visit. The randomization visit should occur with timing of lab results availability and prenatal visit if applicable.

Randomization may occur upon confirmation that all exclusion/inclusion criteria are satisfied and after verification of participant consent and HIPAA authorization. Of particular importance, careful consideration will be given the patient's prior history and medications to determine final eligibility and the appropriate study algorithm to follow (see below). Study staff will also verify participant contact information and obtain a Release of Information.

The MFM Research team will review the following before randomization:

- Complete review of all exclusion and inclusion criteria
- Informed consent obtained
- Iron studies and baseline labs to confirm eligibility
- Pre-intervention survey to assess symptoms

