Patients in both groups will complete post-intervention surveys at 1 week, 4 weeks, and 8-12 weeks after initiating therapy to monitor symptoms and adverse events.

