# 7.3 Management of patient's intolerance to study intervention

#### Oral iron:

For adverse effects, particularly GI, consideration may be given for IV iron as this is standard of care. Per ACOG, intravenous iron is an approved indication for patient's intolerant of oral iron.

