#### Intravenous iron:

For adverse effects such as hypotension (maternal BP<90/60) and persistent dizziness, headaches, lightheadedness or fatigue and no other potential cause other than the medication, will be assessed for adverse reactions and any signs of anaphylaxis. Methylprednisolone, solumedrol, or dexamethasone, albuterol nebulizers, and intramuscular epinephrine will be available on site for any immediate concerns.

PLEASE REFER TO THE DETAILED ALGORTIHM APPROACH FOR MANAGEMENT OF ADVERSE REACTIONS: this is a figure from Rampton, et a "Hypersensitivity reactions to intravenous iron: guidance for risk minimization and management."

For patients that are stable for transfer, the plan will be for obstetric monitoring and further evaluation at the LPCH OB triage on the third floor. The location is across the street from the CTRU and Stanford/LPCH clinic. The patients will still be followed by the study in intent to treat fashion. In the cases of an unstable patient, 911 will be called and patient will be transferred immediately to the emergency room.

To increase effective management of possible hypersensitivity reactions in the IV group: the following have been included.

- Reference range of normal vitals in pregnancy
- Algorithm for management of hypersensitivity reactions

[figure not shown]

Figure 1. Algorithm outlining grading and management of acute hypersensitivity reactions to intravenous iron infusions. Details are given in the text.

- I. Management of mild Hypersensitivity reactions
- II. Mild of Moderate Hypersensitivity reactions
- III. Severe/life threatening Hypersensitivity reactions

Note: Methyl prednisone prior to IV infusion may considered on case by case basis for patients with history of asthma or high risk medication allergy.

Visit Description	Screening/ Enrollment	Treatment		4 weeks	8 weeks	Delivery	1 day	6 weeks
		IV Ferumoxytol	Oral Ferrous sulfate	Post-initiation/ Post- completion	Post-initiation/ Post- completion		Postpartum	postpartum
Visit Window	24-34 weeks GA	24-34 weeks	24-34 weeks GA up to delivery	•	•		1 day after delivery	
Screening of pregnant women with eligible hemoglobin and ferritin levels	X		•					
Review eligibility criteria	X							
Informed consent	X							
Iron studies with or without baseline complete metabolic panel (depending on history of liver or kidney disease)	X							
Randomization	X							
Assign study number	X							
Demographics	X							
Medical and obstetric history review	X							

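### One adverse-event outcome counts only events tied to treatment, with no attribution rule in an open-label trial, and the plan does not say whether it or the unrestricted rate is compared between arms

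*Combined protocol and SAP*

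**What the plan says.** Two places in the combined protocol and SAP define the adverse-event outcome, and they differ.

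- The protocol summary, under the primary safety outcome, lists "Rates of adverse events" with no reference to cause.
- Section 3.2 lists, as a secondary outcome, "the rate of adverse events associated with treatment".

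Section 12.3 promises an intent-to-treat comparison of primary and secondary outcomes but does not mention adverse events by name. Section 12.1 lists efficacy endpoints only.

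On design, section 4.1 states: "This will be an open-label randomized clinical trial at an academic tertiary care center". No section says who decides that an event is associated with treatment, on what scale, or whether that person knows the arm.

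On collection, section 6 requires a "Pre-intervention survey to assess symptoms" before randomization, and then: "Patients in both groups will complete post-intervention surveys at 1 week, 4 weeks, and 8-12 weeks after initiating therapy". Section 10.2 gives examples of reportable events for both arms. Most are serious. One entry covers any event that causes the study drug to be stopped or that is suspected of being caused by it.

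**The concern.** If an outcome counts only events tied to treatment, its rate is the product of two things: how often events occur, and how often someone ties them to the drug. In an open-label trial the second can differ by arm even when the first does not.

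The protocol itself sets unequal expectations. Section 2.2 cites adverse effects in more than 70% of pregnant women on oral iron, section 2.3.2 lists high rates of abdominal pain and nausea with ferrous sulfate, and section 2.2 describes newer IV preparations as well tolerated. The same section notes that oral iron is often abandoned because of side effects. Tolerability is thus part of the case for IV iron, and the adverse-event rate is where it would be shown.

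The gap in section 12.3 adds to this. With two definitions and no rule for choosing, either rate could be presented as the between-arm result after unblinded data collection.

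**Working it through.** **Step 1: is there a figure in the plan to reproduce?** No. The sample size (32 per arm required, 80 to be recruited, 40 per arm) concerns the proportion with hemoglobin below 11 g/dL at birth hospitalization. No adverse-event rate, attribution probability or power is stated for the safety outcome.

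**Step 2: does attribution decide what is counted?**

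| Place | Condition on cause |
|---|---|
| Summary, primary safety outcome | None |
| Section 3.2, adverse-event item | Must be associated with treatment; term undefined |
| Section 3.2, symptom item | None; covers symptoms from before treatment to its end |
| Section 10, serious events | None; defined by consequence |
| Section 10.2, reportable examples | None for most; for ordinary symptoms, mainly drug stopped or drug suspected |

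Attribution therefore governs one secondary outcome and, for ordinary symptoms, much of what section 10.2 names as reportable. Its list is given as examples, so it does not exclude other events.

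**Step 3: what would unequal attribution do?** Let p be the true all-cause rate, equal in both arms, and let a(IV) and a(oral) be the probabilities that an event is tied to treatment. Then

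reported difference (IV minus oral) = p × a(IV) − p × a(oral) = p × [a(IV) − a(oral)].

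For example, with p = 0.50, a(IV) = 0.5 and a(oral) = 0.9: 0.25 − 0.45 = −0.20.

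All values of p and a are assumptions, since the documents give none. The table shows the difference in percentage points. In brackets is the chance of a significant result at 40 per arm (two proportions, normal approximation, two-sided 0.05; section 12.3 gives the 0.05 threshold but not the sidedness).

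| a(IV) | a(oral) | p = 30% | p = 50% | p = 70% |
|---|---|---|---|---|
| 0.8 | 0.8 | 0 (5%) | 0 (5%) | 0 (5%) |
| 0.8 | 0.7 | +3 (5.1%) | +5 (6.7%) | +7 (9.1%) |
| 0.7 | 0.9 | −6 (9.1%) | −10 (14.6%) | −14 (24.0%) |
| 0.5 | 0.9 | −12 (25.8%) | −20 (46.5%) | −28 (71.5%) |

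An all-cause count has an expected difference of 0 throughout.

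**Step 4: what if the arms truly differ?** Take 70% with oral iron (the order of the figure cited in section 2.2) and an assumed 40% with IV iron. The all-cause difference is 0.40 − 0.70 = −30 points. Attribution changes it as follows:

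- 0.8 in both arms: 0.32 − 0.56 = −24 points
- 0.5 IV and 0.9 oral: 0.20 − 0.63 = −43 points
- 0.9 IV and 0.6 oral: 0.36 − 0.42 = −6 points

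The attributed rate can overstate or understate a real difference.

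**The case against.** The strongest reply is that the plan already holds most of the remedy. The summary's adverse-event rate has no causal condition, serious events are defined by consequence, and the visit schedule has adverse-event monitoring in both arms. Section 3.2 also lists patients' symptoms before, during and after treatment as a separate secondary outcome, which section 12.3 would compare. In addition, item j of section 1.1.2 plans blinded review of main outcomes, and the phrase in section 3.2 may mean no more than events occurring under each treatment.

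Much of this stands. It rules out three stronger readings that a reader might infer.

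- *That the whole safety comparison is biased.* Only one listed outcome depends on attribution.
- *That section 7.3 filters the endpoint in the IV arm only.* Its IV paragraph speaks of symptoms with "no other potential cause other than the medication, will be assessed for adverse reactions", and its oral paragraph, "For adverse effects, particularly GI, consideration may be given for IV iron", has no such condition. But section 7.3 concerns management of intolerance. The clause decides which IV patients are assessed for a reaction, names no gastrointestinal symptom, and is not linked to the outcome anywhere.
- *That the analysis ignores the baseline survey.* The symptom outcome includes it, although no counting rule or model is given.

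The reply does not remove the core point. The two definitions still conflict and section 12.3 does not choose between them. The blinded review is not said to cover causality of adverse events. If the phrase in section 3.2 only means events under treatment, saying so costs one sentence.

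**Conclusion.** The point holds as a risk of bias in one secondary outcome, together with an unresolved conflict between the summary and section 3.2. The documents do not show that bias will occur, how large it would be, or which arm it would favor. Under the assumed values in step 3 the spurious difference runs from −28 to +7 points, with a 5% to 72% chance of a false significant result at 40 per arm; it vanishes if attribution is equal and the true rates are equal.

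A reader might infer that IV iron must gain from this. The text does not settle that: section 7.6 describes the IV group's symptom follow-up as additional, which could raise IV counts instead. The point is worth acting on because a better comparison can be specified largely from surveys already planned in both arms.

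**What to change.** State in sections 3.2 and 12.3, and align the summary with them, that:

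1. The main between-arm adverse-event comparison is all-cause. It uses the same survey at 1, 4 and 8-12 weeks in both arms and counts symptoms new or worse than on the pre-intervention survey.
2. Any extra contacts in the IV group do not add to that count.
3. Treatment-related events are supportive only, with one written causality rule for both arms and an assessor unaware of the arm where feasible.
4. Reactions at infusion visits are reported separately.
5. The management text in section 7.3 does not define the endpoint. That text itself stays as it is.

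The survey is not in the documents, so check first that its items match before and after treatment and grade severity. If they do not grade severity, only new symptoms can be counted.

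The cost is wording, plus that check. There are two downsides: all-cause rates carry more background noise from pregnancy, and self-report in an open-label trial keeps its expectation bias. The change removes the attribution step, not the participants' knowledge of their arm.
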